# **SYNOPSIS**

Protocol Title:	The TRANQUILITY 2 Trial: A Multi-Center Randomized, Double-Masked, Parallel Design, Vehicle-Controlled Phase 3 Clinical Trial to Assess the Efficacy and Safety of 0.25% -Reproxalap Ophthalmic Solution Compared to Vehicle in Subjects with Dry Eye Disease	
Protocol Number:	ADX-102-DED-023	
Investigational Product:	0.25% Reproxalap Ophthalmic Solution (reproxalap)	
Study Phase:	3	
Primary Objective(s):	To evaluate the efficacy of reproxalap, as assessed by conjunctival redness, Schirmer's Test, and symptoms after dosing prior to and during exposure to the with dry eye disease	
Overall Study Design:		
Structure:	Multi-center, double-masked, randomized parallel design trial	
Duration:	An individual subject's participation is estimated to be approximately 16-32 days.	
Controls: Vehicle Ophthalmic Solution (vehicle)		
Dosage/Dose Regimen:	Test article (reproxalap or vehicle) will be dosed topically in both eyes.  Test article will be administered QID on Day 1 (Visit 2). On Day 2 (Visit 3), test article will be administered once within 10 minutes prior to the CAE entry, once 45 minutes after initiation of the CAE, and once at CAE exit.	
Summary of Visit Schedule:	Three visits over the course of approximately 2 weeks:  • Visit 1 = Day -14 -16/+2, Screening	

Confidential Page 3 of 60

 
Visit 2 = Day 1, Randomization/Baseline
 
Visit 3 = Day 2 CAE & Study Exit
 
Subjects will be randomized 1:1 to receive reproxalap or vehicle.
 
Measures Taken to Reduce Bias:
 
ADX-102-DED-023 is a randomized treatment assignment, double-masked trial.
 
			
Study Population Characteristics:			
Number of Subjects:	Approximately 350 subjects are expected to be enrolled in the trial.		
Condition/Disease:	Dry Eye Disease (DED)		
Inclusion Criteria:	
 
Subjects must meet all of the following criteria:
 
1. 18 years of age (either gender and any race);
 
2. Ability to provide written informed consent and sign the Health Information Portability and Accountability Act (HIPAA) form;
 
3. Reported history of dry eye for at least 6 months prior to Visit 1;
 
4. Reported history of use or desire to use eye drops for dry eye symptoms within 6 months of Visit 1;
 
		
Exclusion Criteria:	Subjects must not meet any of the following criteria:		

Confidential Page 4 of 60

- 1. Clinically significant slit lamp findings at Visit 1 that may include active blepharitis, meibomian gland dysfunction (MGD), lid margin inflammation, or active ocular allergies that require therapeutic treatment, and/or in the opinion of the investigator may interfere with study parameters;
- 2. Diagnosis of an ongoing ocular infection (bacterial, viral, or fungal), or active ocular inflammation at Visit 1;
- 3. Contact lens use within 7 days of Visit 1 or anticipate using contact lenses during the trial;
- 4. Artificial tear eye drop use within 2 hours of Visit 1 or within 24 hours of Visit 2 (drops cannot be used on the day of Visit 2 or Visit 3);
- 5. Previous laser-assisted *in situ* keratomileusis (LASIK) surgery within the last 12 months;
- 6. Cyclosporine 0.05% or 0.09% or lifitegrast 5.0% ophthalmic solution use within 90 days of Visit 1;
- 7. Systemic corticosteroid or other immunomodulator therapy (not including inhaled corticosteroids) within 14 days of Visit 1 or any planned immunomodulatory therapy throughout the study period;
- 8. Planned ocular and/or lid surgeries over the study period or any ocular surgery within 6 months of Visit 1;
- 9. Temporary punctal plugs during the study that have not been stable within 30 days of Visit 1;
- 10. Use of and unwillingness to discontinue topical ophthalmic prescriptions (including medications for glaucoma) or over-the-counter (OTC) solutions (not including artificial tears), gels, or scrubs for the duration of the trial (excluding medications allowed for the conduct of the trial);
- 11. Corrected visual acuity greater than or equal to logarithm of the minimum angle of resolution

Confidential Page 5 of 60

- (logMAR) + 0.7 as assessed by Early Treatment of Diabetic Retinopathy Study (ETDRS) scale in both eyes at Visit 1;
- 12. Pregnancy, nursing, or planned pregnancy during the conduct of the trial:
- 13. Unwillingness to submit a urine pregnancy test at Visit 1 and Visit 3 (or early termination visit) if of childbearing potential. (Non-childbearing potential is defined as a woman who is permanently sterilized [e.g., has had a hysterectomy or tubal ligation], or is postmenopausal [without menses for 12 consecutive months]);
- 14. If of childbearing potential (female or male), unwillingness to use an acceptable means of birth control. (Acceptable methods of contraception include: hormonal oral, implantable, injectable, or transdermal contraceptives; mechanical spermicide in conjunction with a barrier such as a diaphragm or condom; intrauterine device [IUD]; or surgical sterilization of partner. For non-sexually active males or females, abstinence may be regarded as an adequate method of birth control; however, if the subject becomes sexually active during the study, he/she must agree to use adequate birth control as defined above for the remainder of the trial.);
- 15. Known allergy and/or sensitivity to the test article or its components;
- 16. A condition that the investigator feels may put the subject at significant risk, may confound the study results, or may interfere significantly with the subject's participation in the trial;
- 17. Current enrollment in an investigational drug or device study or have used an investigational drug or device within 30 days of Visit 1;
- 18. Use of reproxalap ophthalmic solution in the past year;

Confidential Page 6 of 60

	

19. Current use of any medication known to cause ocular drying that is not used on a stable dosing regimen for at least 30 days prior to Visit 1;

20. Inability or unwillingness to follow instructions, including participation in all study assessments and visits.

Study Formulations and Formulation Numbers:	0.25% Reproxalap Ophthalmic Solution
Evaluation Criteria:	
Primary Endpoints:	
 
Schirmer's Test overall mean change from baseline (CFB) before and after the fourth dose on Day 1
 
Schirmer's Test greater than or equal to 10mm responder analysis of change from baseline before and after the fourth dose on Day 1
 

Secondary Endpoints:	Overall mean CFB of Conjunctival Redness over 90 minutes in the CAE at Day 2 Overall mean CFB of Eye Dryness (VAS; Visual Analog Scale) over 90 minutes in the CAE at Day 2  Day 2

Confidential Page 7 of 60

	•
	·  
	Overall mean CFB of Conjunctival Redness over Days 1 and 2 (excluding CAE)
	• Change in tear RASP levels before and after Dose 1 and 2 on Day 1 and Dose 3 on Day 2
Evaloustous Endrainte	• Conjunctival redness,
Exploratory Endpoints:	and visual analog scale dryness
	score by time point during the CAE
	Visual acuity
Cafata East 1	

 Slit-lamp evaluation

 Adverse event query

Safety Endpoints:	• Intraocular Pressure (IOP)
	Dilated fundoscopy
General Statistical Methods and T	

Confidential Page 8 of 60

Statistical analyses will be detailed in the statistical analysis plan (SAP), which will dominate any statistical language herein. Any changes to protocol stated analyses will also be detailed in the SAP.

#### Multiplicity Considerations:

To control for multiplicity among primary and secondary endpoints, endpoints will be tested in a fixed sequence at a study-wide two-sided alpha level of 0.05. The primary and secondary endpoints will be tested in the fixed testing sequence as follows:

#### Primary Endpoint:

- 1. Schirmer's Test overall mean change from baseline (CFB) before and after the fourth dose on Day 1
- 2. Schirmer's Test greater than or equal to 10mm responder analysis of change from baseline before and after the fourth dose on Day 1

[figure not shown]
#### Secondary Endpoints:

- 3. Overall mean CFB of Conjunctival Redness over 90 minutes in the CAE at Day 2
- 4. Overall mean CFB of Eye Dryness (VAS; Visual Analog Scale) over 90 minutes in the CAE at Day 2
- 5. Overall mean CFB of Eye Dryness (VAS) assessed over Days 1 and 2 (excluding CAE)

Confidential Page 9 of 60

Formal statistical testing of primary and secondary endpoints in the fixed sequence will halt upon a P-value greater than or equal to 0.05. All remaining endpoints in the sequence will be considered exploratory.
No type I error control will be utilized for exploratory endpoints; thus, exploratory comparisons are considered hypothesis generating.
Sample Size:
Primary Efficacy Analyses:

Confidential Page 10 of 60

Confidential Page 11 of 60

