#### Visit 2 (Day 1, Baseline and In-Office Dosing)

- Medical/Medication Update
- Adverse Event Query
- Visual Acuity (ETDRS)
- Slit Lamp Biomicroscopy
- Symptom Questionnaires
- Conjunctival Redness Photography
- Inclusion/Exclusion Criteria Review
- Randomization/Enrollment
- Pre-Dose #1 Tear Collection (30 +/- 5 minutes pre-dose)
- In-Office Dose #1
- Post-Dose #1 Tear Collection (started within 10 + 2 minutes of dose) *Wait 3 hours between doses*

Confidential Page 26 of 60

- Pre-Dose #2 Tear Collection (30 +/- 5 minutes pre-dose)
- In-Office Dose # 2
- Post-Dose #2 Tear Collection (started within 10 + 2 minutes of dose) Wait 30 minutes between doses
- In-Office Dose #3
- Conjunctival Redness Photography (10 minutes +/- 2 minutes post-Dose #3)
- Symptom Questionnaires started within 10 minutes + 2 minutes post-

Wait 30 minutes between doses

- Pre-Dose #4 Schirmer's Test (10 +/- 2 minutes pre-dose)
  - Weigh Schirmer's Test strip before and after use
- In-Office Dose #4
- Post-Dose #4 Schirmer's Test (started within 5 +/- 2 minutes of dose)
  - Weigh Schirmer's Test strip before and after use
- Schedule for Visit 3

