#### Secondary Endpoints:

- 3. Overall mean CFB of Conjunctival Redness over 90 minutes in the CAE at Day 2
- 4. Overall mean CFB of Eye Dryness (VAS; Visual Analog Scale) over 90 minutes in the CAE at Day 2
- 5. Overall mean CFB of Eye Dryness (VAS) assessed over Days 1 and 2 (excluding CAE)

_	,	,	(	,	3	(	0	,

[figure not shown]
Confidential Page 36 of 60

Confidential Page 37 of 60

Estimand 1	
	_

Confidential Page 38 of 60

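### Is it a flaw that redness and dryness can be confirmed only after both Schirmer's tests, the mean change and the ≥10 mm responder analysis, have succeeded?

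*Combined protocol and SAP*

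**What the plan says.** Under Multiplicity Considerations in the Synopsis, "endpoints will be tested in a fixed sequence at a study-wide two-sided alpha level of 0.05". The order is repeated in section 10.4.4:

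1. Primary: "Schirmer's Test overall mean change from baseline (CFB) before and after the fourth dose on Day 1"
2. Primary: "Schirmer's Test greater than or equal to 10mm responder analysis of change from baseline before and after the fourth dose on Day 1"
3. Secondary: "Overall mean CFB of Conjunctival Redness over 90 minutes in the CAE at Day 2"
4. Secondary: eye dryness on the visual analogue scale during the Day 2 chamber exposure (CAE)
5. Secondary: eye dryness over Days 1 and 2 outside the chamber

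The Synopsis gives the stopping rule: "Formal statistical testing of primary and secondary endpoints in the fixed sequence will halt upon a P-value greater than or equal to 0.05". After a halt, "All remaining endpoints in the sequence will be considered exploratory". Sections 6.1 and 6.3 classify the endpoints in the same way: both Schirmer's analyses are primary, redness and dryness secondary.

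The Synopsis row for the primary objective reads: "To evaluate the efficacy of reproxalap, as assessed by conjunctival redness, Schirmer's Test, and symptoms after dosing prior to and during exposure". Section 2 gives the same sentence as the study objectives, without the word primary.

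The Visit 2 procedures in section 8.3.1 list one Schirmer's assessment before dose 4 and one after it ("Post-Dose #4 Schirmer's Test (started within 5 +/- 2 minutes of dose"). Both primary endpoints draw on these readings.

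**The concern.** The objective names three domains: redness, Schirmer's Test and symptoms. Two of them can be confirmed only if two successive tests of the third both succeed. The second of those tests takes no new measurement; it cuts the same Schirmer's changes at 10 mm. Dichotomising usually loses power, so the trial could show a clear mean effect on Schirmer's, narrowly miss the responder test, and then be unable to confirm redness or dryness whatever their P-values. Two domains would seem to be lost to a second look at a domain already won, while another allocation of the same 0.05 would keep them open.

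**Working it through.** **Step 1. Is type I error controlled?** In a fixed sequence with every step at 0.05, a false claim requires rejecting the first true null in the order. That happens with probability at most 0.05, so the familywise error is at most 0.05, as stated. Five unadjusted independent tests would give 1 − 0.95⁵ = 0.226. The order does its job.

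**Step 2. What does the gate cost?** No effect size, SD, responder rate or power is legible, so these inputs are assumptions:

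- 175 per arm (about 350 randomised 1:1; section 4 says about 150 per arm, which changes the joint pass probabilities below by at most about 4 points)
- one normally distributed change per subject, with a pure shift between arms
- 90% power for test 1
- vehicle responder rate 10%, 20% or 30%
- 80% power for each of tests 3 to 5, independent of Schirmer's

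Worked case, vehicle rate 20%:

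- Standardised shift: d = (1.960 + 1.282) × √(2/175) = 0.347.
- Responder rate on reproxalap: 1 − Φ(0.842 − 0.347) = 0.310.
- Power of the responder test, 31.0% against 20%: 0.66.
- Both Schirmer's tests won, simulated on the same data: 0.65.
- Redness confirmed as planned: 0.65 × 0.80 = 0.52.
- Test 1 won but test 2 missed: 0.90 − 0.65 = 0.25. This is the outcome the concern is about.

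**Step 3. What would an alternative gain?** Suppose test 1 is run at 0.05 and, if won, the responder test at 0.025 runs in parallel with tests 3, 4 and 5 in order at 0.025. A fully won branch passes its 0.025 to the other.

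- Redness power at 0.025: Φ(1.960 + 0.842 − 2.241) = 0.71.
- Test 1 and the responder test at 0.025 both won: about 0.55.
- Redness confirmed: 0.55 × 0.80 + (0.90 − 0.55) × 0.71 = 0.69.
- Familywise error when test 1 has a true effect and the rest are null, taken as independent: 1 − 0.975² = 0.049.

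Simulated results:

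| Assumed case | Redness, plan | Redness, split | Gain (points) | Responder, plan | Responder, split |
|---|---|---|---|---|---|
| Test 1 at 90%, vehicle rate 10% | 0.42 | 0.67 | 25 | 0.53 | 0.45 |
| Test 1 at 90%, vehicle rate 20% | 0.52 | 0.69 | 17 | 0.65 | 0.59 |
| Test 1 at 90%, vehicle rate 30% | 0.57 | 0.70 | 13 | 0.71 | 0.64 |
| Effect confined to a subgroup, case A | 0.709 | 0.723 | 1.4 | 0.883 | 0.868 |
| Subgroup, case B | 0.629 | 0.681 | 5.2 | 0.785 | 0.745 |
| Subgroup, case C | 0.616 | 0.677 | 6.1 | 0.770 | 0.727 |

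The subgroup cases assume that 20–25% of subjects gain 10 mm, with SD 5–7 mm. With test 1 at only 80% power, redness moves from 0.32, 0.41 and 0.46 to 0.59, 0.61 and 0.61 at the three vehicle rates, gains of 27, 20 and 15 points.

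**Step 4. How far does the gain depend on unseen sizing?** The large gains assume a trial powered for test 1 while test 2, also a listed primary, is left at 0.54–0.72 (lower still with test 1 at 80%). If the trial was sized so that the responder test has about 0.89–0.92 power, the same shift model gives redness 0.71 rising to 0.78, or 0.74 rising to 0.79: gains of 7 and 5 points. Drops go in both eyes and readings are taken before and after dose 4, so up to four Schirmer's readings per subject could enter. With four readings at an assumed correlation of 0.4–0.6 and test 1 at 90%, the gain is about 7–18 points.

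**Step 5. Is the responder test redundant?** Under the shift model the two Schirmer's statistics correlate at 0.62–0.78, not 1. The mean change asks how far the average moved; the responder analysis asks how many subjects reached a set threshold. A plan may reasonably require both.

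**The case for a change.** The strongest case for changing the order is that its structural premise is right and needs no assumption: if test 1 succeeds and test 2 fails, redness and dryness cannot be confirmed. Dryness is gated further, because it also needs redness to succeed. Under a pure shift with 90% power for test 1, that first combination has probability about 0.19 to 0.37 (0.90 minus 0.71, 0.65 or 0.53), which is not negligible. The split controls error equally well and needs no new data. No reason for the order is legible, and no primary endpoint measures redness or symptoms although the Synopsis objective names them.

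The structural fact and the arithmetic stand. They do not make the order wrong. The split takes alpha from a listed primary to fund secondaries, and it permits a confirmed secondary beside a failed primary, which many sponsors would not want. In the subgroup cases the gain on redness is close to the loss on the responder endpoint: 1.4 against 1.5 points, 5.2 against 4.0, and 6.1 against 4.3. The wording of the objective is an editorial matter, since all three domains already have a place in the alpha-controlled sequence. Writing down a reason for the order would change no result.

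The protocol also says that the SAP overrides its statistical text, and no separate SAP text is available. A different order there cannot be excluded, but both legible statements of the sequence agree.

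**Conclusion.** The concern does not hold. Requiring both listed primary endpoints to succeed before any listed secondary is tested is conventional gatekeeping. It keeps the familywise error at 0.05, and whatever it confirms is sound. Its price is a lower chance of confirming redness and dryness than under a split allocation. For redness the difference is 1 to 6 points if the effect sits in a subgroup, about 5 to 7 points if the trial was sized on the responder test, and 13 to 27 points under a pure shift with 80–90% power for the mean-change test and vehicle responder rates of 10–30%. Against that stand about 2 to 8 points lost on a primary endpoint and a weaker hierarchy of claims. All these figures rest on assumed powers, rates and independence, because the sample-size text is not legible. Reasonable statisticians could choose either allocation, so the plan needs no correction on this point.

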#### List of Abbreviations

AE adverse event

CFR Code of Federal Regulations

DED dry eye disease DES dry eye syndrome

DHHS Department of Health and Human Services
ETDRS Early Treatment of Diabetic Retinopathy Study

FDA Food and Drug Administration

GCP Good Clinical Practice

HIPAA Health Information Portability and Accountability Act

ICF informed consent form

ICH International Council for Harmonisation

IEC Independent Ethics Committee

IRB institutional/independent review board

LogMAR logarithm of the minimum angle of resolution

OTC over the counter

RASP reactive aldehyde species SAE serious adverse event

μL microliter
VA visual acuity

VAS Visual analog scale

Confidential Page 15 of 60

#### 1 INTRODUCTION

Dry eye disease (DED) is the most prevalent form of ocular discomfort and irritation. The estimated population of individuals with mild to moderate DED ranges from 20 million Americans up to 1 out of every 5 Americans. DED can be related to external environmental factors such as low humidity in air-conditioned offices, winter heating, and dusty or windy outdoor environments. Behaviors including prolonged computer use and wearing contact lenses, and internal factors such as hormonal imbalance, autoimmune disease, systemic medications, anatomical changes, trauma, and aging are also contributors. Symptoms result in a mildly decreased quality of life at a minimum and, with increasing severity, loss of function and productivity, pain, light sensitivity, and emotional distress. The aging population in the United States and in other developing countries, and increasing computer use will continue to make DED more prevalent (Schaumberg et al, 2009).

Given that there are few substantive treatments for DED, various over-the-counter (OTC) products are available to help provide temporary relief for DED and for all of the tear film abnormalities. OTC products aim to alleviate symptoms by replacing or retaining moisture on the ocular surface. Additionally, some artificial tear products contain demulcents to enhance lubrication. OTC products provide only short-lived action at best necessitating frequent dosing throughout the day.

Confidential Page 16 of 60

# 2 STUDY OBJECTIVES

To evaluate the efficacy of reproxalap, as assessed by conjunctival redness, Schirmer's Test, and symptoms after dosing prior to and during exposure to the (CAE) in subjects with dry eye disease.

# 3 CLINICAL HYPOTHESES

The clinical hypothesis is that reproxalap is more effective than vehicle in reducing the signs and symptoms of DED.

Confidential Page 17 of 60

#### 4 OVERALL STUDY DESIGN

ADX-102-DED-023 is a Phase 3, multi-center, randomized, double-masked, parallel design, vehicle-controlled trial designed to evaluate the efficacy and safety of 0.25% Reproxalap Ophthalmic Solution compared to vehicle in subjects with dry eye disease. Approximately 350 subjects will be enrolled in the study. Male and female subjects at least 18 years of age with a subject-reported history of dry eye disease in both eyes and meeting all other eligibility criteria will be randomized to receive reproxalap or vehicle in a 1:1 ratio (approximately 150 subjects in each treatment group).

Visit 1 (Day -14 -16/+ 2): Screening	
 
Informed Consent
 
Demographics, Medical/Medication & Ocular History
 
Urine Pregnancy Testing (as needed)
 
Symptom Questionnaires, Ocular Dryness VAS, Visual Acuity
 
Slit Lamp Exam with Conjunctival Redness assessment
 
CAE exposure (90 minutes) with Ocular Dryness VAS, and Conjunctival Redness Assessment
 
Slit Lamp Exam with Conjunctival Redness assessment
 
Schirmer's Test
 
IOP and Dilated Fundoscopy
 

Visit 2 (Day 1): Randomization/Baseline	
 
Medical/Medication Update: AE Query
 
Visual Acuity
 
Slit Lamp Exam
 
Symptom Questionnaires at specified time points
 
Conjunctival Redness at specified time points
 
In-Office Doses (QID)
 
Tear Collection & Schirmer's Test at specified time points
 

Visit 3 (Day 2): CAE	
 
Medical/Medication Update: AE Query
 
Urine Pregnancy Testing (as needed)
 
Visual Acuity, Slit Lamp Exam
 
Symptom Questionnaires
 
Conjunctival Redness at specified time points
 

Confidential Page 18 of 60

CAE exposure (90 minutes) with Ocular Dryness
VAS, and and
Conjunctival Redness Assessments
Tear Collection at specified time points
IOP and Dilated Fundoscopy
Study Exit

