#### 5 STUDY POPULATION

# 5.1 Number of Subjects (approximate)

Approximately 600 subjects will be screened to enroll approximately 350 subjects across approximately 17 sites.

[figure not shown]

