#### 7 STUDY MATERIALS

# 7.1 Study Treatment(s)

#### 7.1.1 Formulations

Randomized Study Treatments

- 0.25% Reproxalap Ophthalmic Solution
- Vehicle

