#### 10 STATISTICAL HYPOTHESES AND METHODS OF ANALYSES

#### **10.1 Analysis Populations**

[figure not shown]
The following analysis populations will be considered:

- Intent-to-Treat Population The intent-to-treat (ITT) population includes all randomized subjects. Subjects in the ITT population will be analyzed as randomized.
- Per-Protocol Population The per-protocol (PP) population includes subjects in the ITT population who do not have significant protocol deviations and who complete the study. Protocol deviations will be assessed prior to database lock and unmasking. Subjects in the PP population will be analyzed as treated.
- Safety Population The safety population includes all randomized subjects who have received at least one dose of the investigational product. Subjects in the safety population will be analyzed as treated.

Confidential Page 34 of 60

All analyses will be performed for the ITT population and, in addition, on the PP population as sensitivity analyses, as needed. Descriptive statistics of safety data will be calculated for the safety population.

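### Section 4 plans about 350 enrolled but about 150 per arm at 1:1, which makes 300; the visible text does not explain the difference of 50

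*Combined protocol and SAP*

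**What the plan says.** Section 4 (Overall Study Design) gives the total first: "Approximately 350 subjects will be enrolled in the study". The following sentence says that eligible subjects will be "randomized to receive reproxalap or vehicle in a 1:1 ratio (approximately 150 subjects in each treatment group".

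The total appears in two other places. The Synopsis says "Approximately 350 subjects are expected to be enrolled in the trial", and Section 5.1 says "Approximately 600 subjects will be screened to enroll approximately 350 subjects across approximately 17 sites". The count per group appears only once, in the Section 4 parenthesis.

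The rest of the visible design is consistent. The Synopsis states "Subjects will be randomized 1:1 to receive reproxalap or vehicle", Section 8.1.5 repeats the 1:1 ratio, and Section 7.1.1 lists two items under "Randomized Study Treatments": reproxalap and vehicle. The Visit 2 procedures in Section 8.3.1 show a single entry, "Randomization/Enrollment".

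The sample size text itself cannot be read in the public copy. The Synopsis has the heading with nothing under it, and Section 10.3 is in the table of contents but has no visible body.

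**The concern.** Two adjacent sentences give a total and a count per group that do not agree in a two-arm 1:1 trial. A reader of Section 4 cannot tell whether the number to be randomized is 300 or 350, or whether 150 counts something else, such as evaluable subjects.

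The planned number randomized is a basic design figure in a Phase 3 trial, and the screening plan is built on it, so it should read the same way throughout. The point goes no further than that. No visible test, alpha rule or population definition uses the count per group.

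**Working it through.** **Inputs**

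| Quantity | Value | Where |
|---|---|---|
| Total enrolled | about 350 | Synopsis; Section 4; Section 5.1 |
| Per treatment group | about 150 | Section 4 only |
| Arms and ratio | 2 arms, 1:1 | Synopsis; Sections 4, 7.1.1, 8.1.5 |
| Screened | about 600 | Section 5.1 |
| Enrolment and randomization | one step at Visit 2 | Section 8.3.1 |

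**Trying to reproduce the plan's figures**

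At 1:1 in two arms, total = 2 × number per group.

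- From the count per group: 2 × 150 = 300, not 350.
- From the total: 350 / 2 = 175, not 150.
- Gap in total: 350 − 300 = 50. Gap per group: 175 − 150 = 25.
- Relative gap: 50 / 350 = 25 / 175 = 14.3%.

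Neither figure reproduces the other.

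**Explanations tested against the visible text**

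1. *Rounding.* Both figures are approximate, but 175 does not round to 150. Even a 3% tolerance allows only 0.03 × 350 = 10.5 subjects, against a gap of 50.
2. *Screen failures.* Section 5.1 counts the 600 screened separately from the 350 enrolled, so screen failures are already outside the 350.
3. *Enrolled but not randomized.* Visit 2 makes the two a single step, so 350 enrolled should mean 350 randomized.
4. *A third arm or unequal allocation.* Only two arms are described, and the ratio is 1:1 wherever it is given.
5. *A dropout allowance, with 150 meaning evaluable per group.* The visible text gives no rate, so any rate is an assumption. With total = 300 / (1 − d):

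| Assumed d | 300 / (1 − d), rounded up |
|---|---|
| 5% | 316 |
| 10% | 334 |
| 15% | 353 |
| 20% | 375 |

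Reaching exactly 350 needs d = 1 − 300/350 = 14.3%, so an allowance of about 15% would close the gap. Section 10.1 has a population that 150 could refer to: the per-protocol set, defined as "subjects in the ITT population who do not have significant protocol deviations and who complete the study". But the Section 4 sentence attaches 150 to subjects being randomized, so on this reading its wording is still wrong.

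**Screening figure under each total**

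- 350 / 600 = 58.3% yield.
- 300 / 600 = 50.0% yield.

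**What cannot be computed**

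The visible text gives no effect size, standard deviation, target power or dropout rate, so neither 300 nor 350 can be checked against a power calculation.

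**The case against.** The strongest reply is that the text that would settle the matter is withheld. Both places for the sample size justification are unreadable, and the protocol says that the SAP takes precedence on statistical matters. The full plan may state that 150 is an evaluable count and give the attrition behind it. This stands as a limit: it cannot be said that the plan as a whole leaves the numbers unreconciled, or which figure is wrong. It does not rescue the Section 4 sentence, because no hidden text can make two randomized groups of 150 total 350.

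A second reply is that the visible evidence leans towards 350. That figure appears three times, including in the section devoted to subject numbers, while 150 appears once in a parenthesis. The lean is real and makes a correction to about 175 the most direct repair. It is not proof, since the count per group may be the figure carried over from the power calculation.

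A third reply is that nothing depends on the parenthesis: assignment runs through the IWRS, and the ITT population is whoever is randomized. That is correct, and it is why no effect on the analysis is claimed. It also stands that the two screening yields are not a second discrepancy. No planned yield is stated, and they matter only as something to recheck if the total changes. Finally, the 14.3% is only the gap restated as attrition. Treatment runs only from Day 1 to study exit on Day 2, so a loss of that size would need its own justification.

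**Conclusion.** The concern holds. Section 4 contradicts itself on the number to be randomized: about 350 in total against about 150 in each of two equal groups, or 300. The difference is 50 subjects, 25 per group, 14.3% of the stated total. No visible text closes it, and on every reading at least one visible statement needs correcting.

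This rests on two arms at 1:1 and on enrolment and randomization being the same event, both of which the protocol states. Which figure is intended cannot be determined from the public copy, and no consequence for power is shown. The item should be fixed because a sample size is a figure the trial relies on, but it is a correction of wording and does not challenge the analysis.

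**What to change.** Check the figures against the full sample size section, then make one of three changes:

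1. If 350 is the randomized target, change the Section 4 parenthesis to about 175 per group.
2. If 150 per group is the randomized target, change the totals in the Synopsis, Section 4 and Section 5.1 to about 300, and check whether 600 screened still applies (50.0% yield instead of 58.3%).
3. If 150 is an evaluable count, label it so in Section 4, name the population it refers to, and state the attrition assumed (14.3% if 350 are randomized), with a reason for that rate over a two-day treatment period.

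In each case, say whether each number counts randomized or evaluable subjects. The cost is wording only: one parenthesis under options 1 and 3; three totals and a check of the screening figure under option 2.
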